6.5. Concomitant Therapy

Participants will abstain from all concomitant treatments, except for the treatment of AEs.

Use of prescription or nonprescription drugs and dietary and herbal supplements are prohibited within 7 days or 5 half-lives (whichever is longer) prior to the first dose of study intervention. Limited use of nonprescription medications that are not believed to affect participant safety or the overall results of the study may be permitted on a case-by-case basis following approval by the sponsor. Acetaminophen/paracetamol may be used at doses of ≤ 3 g/day.

Use of medications that prolong the QT interval (a list of these medications can be found at <http://www.crediblemeds.org/index.php/login/dlcheck>) are prohibited within 10 days or 5 half-lives (whichever is longer) prior to the first dose of the study intervention, or during the study.

Vaccination with live virus, attenuated live virus, or any live viral components are prohibited within the 6 weeks prior to the first dose of study intervention. (Refer to [Section 5.3.5](#) for additional details).

Hormonal contraceptives that meet the requirements of this study are allowed to be used in participants who are WOCBP (see [Appendix 4](#)).

All concomitant treatments taken during the study must be recorded with indication, daily dose, and start and stop dates of administration. Concomitant drug and non-drug treatment will be collected. All participants will be questioned about concomitant treatment at each clinic visit.

Treatments taken within 28 days before the first dose of study intervention will be documented as a prior treatment. Treatments taken after the first dose of study intervention will be documented as concomitant treatments.

6.5.1. Rescue Medicine

There is no rescue therapy to reverse the AEs observed with ritlecitinib (PF-06651600); standard medical supportive care must be provided to manage the AEs.

6.6. Dose Modification

Dose modification for ritlecitinib (PF-06651600) is not allowed.

6.7. Intervention After the End of the Study

No intervention will be provided to study participants at the end of the study.

7. DISCONTINUATION OF STUDY INTERVENTION AND PARTICIPANT DISCONTINUATION/WITHDRAWAL

7.1. Discontinuation of Study Intervention

In rare instances, it may be necessary for a participant to permanently discontinue study intervention (definitive discontinuation). Reasons for definitive discontinuation of study intervention include the following: treatment-related SAEs, serious infections, and other events as described in [Section 10.8.2](#).

Note that discontinuation of study intervention does not represent withdrawal from the study. If study intervention is definitively discontinued, the participant will remain in the study to be evaluated for safety. See the [SoA](#) for data to be collected at the time of discontinuation of study intervention and follow-up for any further evaluations that need to be completed.

In the event of discontinuation of study intervention, it must be documented on the appropriate CRF/in the medical records whether the participant is discontinuing further receipt of study intervention or also from study procedures, posttreatment study follow-up, and/or future collection of additional information.

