1.3. Schedule of Activities

The SoA table provides an overview of the protocol visits and procedures. Refer to the **STUDY ASSESSMENTS AND PROCEDURES** section of the protocol for detailed information on each procedure and assessment required for compliance with the protocol.

The investigator may schedule visits (unplanned visits) in addition to those listed in the SoA table, in order to conduct evaluations or assessments required to protect the well-being of the participant.

Visit Identifier Abbreviations used in this table may be found in Appendix 10	Screening ^a	Treatment Period								Follow-up ^b	Early Termination/ Discontinuation
		Period 1		Period 2		Period 3					
Days Relative to Day 1	Day -28 to Day -2	Day -1	Day 1	Day 2	Day 1	Day 2	Day 1	Day 2	Telephone Contact		
Study Day	-28 to -2	-1	1	2	3	4	5	6	33 to 40		
Informed consent	X										
CRU confinement		X	→	→	→	→	→	X			
Inclusion/exclusion criteria	X	X ^c									
Demographic information ^d	X										
Medical/medication, drug, tobacco and alcohol history (update) ^e	X	X ^c									
Complete/limited physical examination ^f	X	X						X		X	
Safety laboratory ^g	X	X						X		X	
Pregnancy test (WOCBP only)	X	X						X		X	
Contraception check ^h	X	X						X	X	X	
FSH (post-menopausal women only)	X										
Urine drug testing	X	X									
12-Lead ECG ⁱ	X		X ^o					X		X	
Blood pressure and pulse rate, temperature ^j	X		X ^o					X		X	
HIV, HCVAb, HBsAg, HbcAb ^k	X										

Visit Identifier Abbreviations used in this table may be found in Appendix 10	Screening ^a	Treatment Period								Follow-up ^b	Early Termination/ Discontinuation
		Period 1		Period 2		Period 3					
Days Relative to Day 1	Day -28 to Day -2	Day -1	Day 1	Day 2	Day 1	Day 2	Day 1	Day 2	Telephone Contact		
Study Day	-28 to -2	-1	1	2	3	4	5	6	33 to 40		
TB screening (QuantiFERON® Gold Test)	X										
Lipid panel ^g	X										
Study intervention administration ^l			X		X ^p		X ^p				
Taste assessment							X ^q				
Pharmacokinetic blood sampling ^m			X	X	X	X	X	X			
Pfizer Prep D1 Banked Genetic Biospecimens ⁿ			X ^o								
Prior/concomitant treatments	X	X	X						X	X	X
CRU discharge									X		
Serious and nonserious adverse event monitoring	X	X	→	→	→	→	→	X	X	X	

- a. Participants will be screened within 28 days of the first dose of study intervention.
- b. Follow-up contact will occur by telephone and must occur at least 28 to 35 days after the last administration of ritlecitinib (PF-06651600).
- c. Update since screening, if applicable.

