4.4. End of Study Definition

A participant is considered to have completed the study if he/she has completed all phases of the study, including the last scheduled procedure shown in the [SoA](#) and the investigator has reviewed the final safety data and determined that no additional evaluation is required.

The end of the study is defined as the date of last scheduled procedure shown in the [SoA](#) for the last participant in the study.

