7.2. Participant Discontinuation/Withdrawal From the Study

A participant may withdraw from the study at any time at his/her own request. Reasons for discontinuation from the study include the following:

- Refused further follow-up;
- Lost to follow-up;
- Death;
- Study terminated by sponsor;
- Adverse Event

At the time of discontinuing from the study, if possible, an early discontinuation visit should be conducted. See the [SoA](#) for assessments to be collected at the time of study discontinuation and follow-up and for any further evaluations that need to be completed.

The early discontinuation visit applies only to participants who are enrolled/randomized and then are prematurely withdrawn from the study. Participants should be questioned regarding their reason for withdrawal. The participant will be permanently discontinued both from the study intervention and from the study at that time.

If a participant withdraws from the study, he/she may request destruction of any remaining samples taken and not tested, and the investigator must document any such requests in the site study records and notify the sponsor accordingly.

If the participant withdraws from the study and also withdraws consent (see Section 7.2.1) for disclosure of future information, no further evaluations should be performed and no additional data should be collected. The sponsor may retain and continue to use any data collected before such withdrawal of consent.

When a participant withdraws from the study because of an SAE, the SAE must be recorded on the CRF and reported on the CT SAE Report.

Lack of completion of all or any of the withdrawal/early termination procedures will not be viewed as protocol deviations so long as the participant's safety was preserved.

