10.8.2. Participant Discontinuation Criteria

Treatment will be discontinued and the participant withdrawn from this study for:

Adverse Events:

- Serious infections, defined as any infection (viral, bacterial, and fungal) requiring parenteral antimicrobial therapy or hospitalization for treatment or meeting other criteria that require the infection to be classified as serious adverse event;
- Treatment related SAEs;
- Other serious or severe AEs, at the discretion of the investigator or sponsor.

ECG Abnormalities

- Confirmed QTcF >500 milliseconds;
- Confirmed increase from baseline in QTcF of >60 milliseconds.

Laboratory Abnormalities:

- All the following laboratory abnormalities require discontinuation if they are confirmed:
 - Absolute Neutrophil Count <750/mm³ (<0.75 × 10⁹/L);
 - Hemoglobin <9.0 g/dL (<5.59 mmol/L or <90 g/L) or a decrease of >30% from baseline (either criterion or both);
 - Platelet count <75,000/mm³ (<75.0 × 10⁹/L);
 - Absolute Lymphocyte Count <500/mm³ (<0.5 × 10⁹/L);
 - Creatine kinase >10 × ULN.

NOTE: In addition to retesting creatine kinase >3 × ULN, urine myoglobin will be performed as reflex testing for any participant with creatine kinase >10 × ULN.

- AST or ALT that meet ANY of the following:
 - >3 times ULN with at least one total bilirubin value >2 times ULN;
 - >3 times ULN accompanied by signs or symptoms consistent with hepatic injury (eg, new onset elevated PT/INR);

- Two sequential AST or ALT elevations >5 times ULN, regardless of total bilirubin or accompanying signs or symptoms.

NOTE: In each case, there is a need for additional investigations, such as review of ethanol, recreational drug and dietary supplement consumption; testing for acute hepatitis A, B or C infection and biliary tract imaging should be promptly discussed with the sponsor or designee.

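### Does the conflict between Protocol Sections 7.1 and 10.8.2 over study status after a safety stop call for a change to the plan?

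*Protocol*

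**What the plan says.** Protocol Section 7.1 lists treatment-related SAEs, serious infections and the other Section 10.8.2 events as reasons to stop study intervention for good. It adds "Note that discontinuation of study intervention does not represent withdrawal from the study", and gives the status after the stop: "If study intervention is definitively discontinued, the participant will remain in the study to be evaluated for safety". It also asks the site to record "whether the participant is discontinuing further receipt of study intervention or also from study procedures".

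Protocol Section 10.8.2 opens its list of criteria with "Treatment will be discontinued and the participant withdrawn from this study for".

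Protocol Section 7.2 includes adverse events among the reasons for leaving the study. It says of a participant who leaves: "The participant will be permanently discontinued both from the study intervention and from the study at that time". On the exit visit it says: "The early discontinuation visit applies only to participants who are enrolled/randomized and then are prematurely withdrawn from the study".

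Protocol Section 4.4 defines completion: "A participant is considered to have completed the study if he/she has completed all phases of the study", up to the last scheduled procedure.

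**The concern.** Section 7.1 borrows its triggers from Section 10.8.2 and then gives the opposite status. Both sentences are directive, no rule says whether body or appendix prevails, and a site cannot record one person as both remaining and withdrawn.

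Three things could hang on the answer:

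- **Procedures after the stop.** A withdrawn participant gets the Early Termination/Discontinuation column of the Schedule of Activities (SoA), which has no entry in the row "Pharmacokinetic blood sampling". If the participant remains, one could argue that the PK samples still due for a dose already taken, and the Study Day 6 safety set, are still required.
- **Disposition.** A participant who goes through every remaining SoA item might be called completed under Section 4.4 and withdrawn under Section 10.8.2.
- **Precision.** With 12 participants, a truncated profile whose AUC cannot be derived costs one within-participant comparison.

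The participants affected would be those with the most serious safety events, so unclear follow-up deserves a check.

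**Working it through.** The plan gives no figure on this point, so the check compares the texts and then bounds the size.

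**1. What each reading requires**

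| Item | Remains (7.1) | Withdrawn (10.8.2 with 7.2) |
|---|---|---|
| Further dosing | None | None |
| Assessments at the stop | SoA; one combined column | SoA; the same column |
| AE/SAE collection, at least 28 days after last dose (8.3.1) | Yes | Yes, unless consent for future information is also withdrawn |
| Telephone contact (SoA footnote b) | Yes | Yes |
| Follow-up of known events (8.3.3) | Yes | Yes |
| Repeat ECG (8.2.3), repeat laboratory tests (8.2.4, 10.8.1) | Yes | Yes |
| Replacement (9.2) | Possible | Possible |
| Second safety set on Study Day 6; rest of current PK profile | Arguable | No |

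Only the last row differs. The argument for it rests on the Section 7.1 instruction about what to record on the CRF, which is not a schedule. The same section says the stay is for safety evaluation and points to SoA data at discontinuation and follow-up, which can equally be read as leaving these items out.

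**2. Safety rows.** Six rows fall on Study Day 6: physical examination, safety laboratory, pregnancy test, contraception check, ECG, and blood pressure/pulse/temperature. All six also have an entry in the Early Termination/Discontinuation column, so they are scheduled at the stop. What is in doubt is a second set. Two of the six (pregnancy test and contraception check) concern women of childbearing potential, which leaves four for everyone else.

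**3. When a criterion can be met.** Section 10.8.2 has 3 AE + 2 ECG + 8 laboratory = 13 criteria. For the 10 ECG and laboratory criteria, the only scheduled test after dosing is at Period 3 Day 2, when all doses have been given and the Study Day 6 set is itself being collected. An earlier stop needs an AE criterion or an unscheduled test.

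**4. Disposition.** One participant is 1/12 = 8.3%. Section 4.4 requires all phases of the study. Someone stopped after dose 1 or 2 misses two or one dosing periods and is hard to call completed on any reading. The double status is essentially confined to stops after dose 3.

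**5. PK samples.** Post-dose times are 0.25, 0.5, 1, 1.5, 2, 3, 4, 6, 9, 12, 16 and 24 h, so 12 per period. Still due after a stop just past 2 h: 7; past 4 h: 5; past 9 h: 3.

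**6. Upper bound on precision.** Take the half-width of the log-scale 90% interval in units of the within-participant SD, using complete pairs only.

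- B/A, 6 + 6: t(0.95, 10) × √(0.5 × (1/6 + 1/6)) = 0.740. With 6 + 5: t(0.95, 9) × √(0.5 × (1/6 + 1/5)) = 0.785. Ratio 1.061.
- C/A, 12 pairs: t(0.95, 11) × √(2/12) = 0.733. With 11: t(0.95, 10) × √(2/11) = 0.773. Ratio 1.054.

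The SD cancels from both ratios. Where the loss could depend on status is narrow:

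- **Stop in Period 1:** both pairs are lost either way, because no further dose is given.
- **Stop in Period 2:** C/A is lost either way; only B/A can depend on status.
- **Stop in Period 3:** only C/A can depend on status.

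In the last two cases the stop must come within 24 h of dosing and before AUC can be derived.

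**7. What the analyst does.** Neither PK analysis set (SAP 5.1.1, 5.1.2) refers to study status. Under SAP 7.3 a parameter that cannot be derived is set to missing, and a known biased estimate is left out of summaries and models. SAP 8.3.3 reports discontinuations. The models in SAP 8.2.1 are the same under both readings.

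**The case for a change.** The best case for a change is that the conflict is explicit, nothing else in the protocol resolves it, and a sentence would cure it. There is also a difference in enforceability. For a withdrawn participant the exit visit is to be held if possible, and Section 7.2 does not count missed withdrawal procedures as deviations so long as safety was preserved; Section 7.1 gives no such waiver to someone who remains. Section 7.2.1 sharpens the contrast: a participant who simply asks to stop dosing stays in the study, whereas Section 10.8.2 withdraws one with a treatment-related SAE. Section 7.2 also limits the early discontinuation visit to withdrawn participants, while Section 7.1 refers those who remain to the SoA for discontinuation data.

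The textual conflict stands, and so does the softer obligation to hold the exit visit. The practical consequence is weak. AE/SAE collection, the telephone contact and the repeat testing come from Section 8.3.1, SoA footnote b and Sections 8.2.3, 8.2.4 and 10.8.1, so they do not rest on the exit visit. A limit on a visit and a pointer to SoA data can coexist, since one SoA column serves both. A rewording that leaves the choice of status to the sponsor would improve no estimate, reduce no bias and add no identified safety protection.

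**Conclusion.** The concern describes a genuine inconsistency, but no change to the plan follows because there is no demonstrable gain. Sections 7.1, 7.2 and 10.8.2 should be reconciled as an editorial matter; I take no position on which status is right or which items should remain due. Dosing stops either way, and the assessments at the stop and the continuing safety follow-up are the same in substance.

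The residue is small: a recorded status for 1 of 12 participants (8.3%), essentially only after dose 3; a possible second safety set after an earlier stop; and at most a 6% (B/A) or 5% (C/A) wider log-scale interval per participant, before any replacement. This rests on three assumptions: the combined SoA column applies to both kinds of stop, as its title indicates; consent for future information is not withdrawn; and such stops are uncommon. The documents give no event rate, though Section 7.1 describes these cases as rare.

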7.2. Participant Discontinuation/Withdrawal From the Study

A participant may withdraw from the study at any time at his/her own request. Reasons for discontinuation from the study include the following:

- Refused further follow-up;
- Lost to follow-up;
- Death;
- Study terminated by sponsor;
- Adverse Event

At the time of discontinuing from the study, if possible, an early discontinuation visit should be conducted. See the [SoA](#) for assessments to be collected at the time of study discontinuation and follow-up and for any further evaluations that need to be completed.

The early discontinuation visit applies only to participants who are enrolled/randomized and then are prematurely withdrawn from the study. Participants should be questioned regarding their reason for withdrawal. The participant will be permanently discontinued both from the study intervention and from the study at that time.

If a participant withdraws from the study, he/she may request destruction of any remaining samples taken and not tested, and the investigator must document any such requests in the site study records and notify the sponsor accordingly.

If the participant withdraws from the study and also withdraws consent (see Section 7.2.1) for disclosure of future information, no further evaluations should be performed and no additional data should be collected. The sponsor may retain and continue to use any data collected before such withdrawal of consent.

When a participant withdraws from the study because of an SAE, the SAE must be recorded on the CRF and reported on the CT SAE Report.

Lack of completion of all or any of the withdrawal/early termination procedures will not be viewed as protocol deviations so long as the participant's safety was preserved.

7.2.1. Withdrawal of Consent

Participants who request to discontinue receipt of study intervention will remain in the study and must continue to be followed for protocol-specified follow-up procedures. The only exception to this is when a participant specifically withdraws consent for any further contact with him or her or persons previously authorized by the participant to provide this information. Participants should notify the investigator in writing of the decision to withdraw consent from future follow-up, whenever possible. The withdrawal of consent should be explained in detail in the medical records by the investigator, as to whether the withdrawal is only from further receipt of study intervention or also from study procedures and/or posttreatment study follow-up, and entered on the appropriate CRF page. In the event that vital status (whether the participant is alive or dead) is being measured, publicly available information should be used to determine vital status only as appropriately directed in accordance with local law.

7.3. Lost to Follow up

A participant will be considered lost to follow-up if he or she repeatedly fails to return for scheduled visits and is unable to be contacted by the study site.

The following actions must be taken if a participant fails to return to the clinic for a required study visit:

- The site must attempt to contact the participant and reschedule the missed visit as soon as possible and counsel the participant on the importance of maintaining the assigned visit schedule and ascertain whether or not the participant wishes to and/or should continue in the study;
- Before a participant is deemed lost to follow-up, the investigator or designee must make every effort to regain contact with the participant (where possible, 3 telephone calls and, if necessary, a certified letter to the participant's last known mailing address or local equivalent methods). These contact attempts should be documented in the participant's medical record;
- Should the participant continue to be unreachable, he/she will be considered to have withdrawn from the study.

8. STUDY ASSESSMENTS AND PROCEDURES

The investigator (or an appropriate delegate at the investigator site) must obtain a signed and dated ICD before performing any study-specific procedures.

Study procedures and their timing are summarized in the [SoA](#). Protocol waivers or exemptions are not allowed.

Safety issues should be discussed with the sponsor immediately upon occurrence or awareness to determine whether the participant should continue or discontinue study intervention.

Adherence to the study design requirements, including those specified in the [SoA](#), is essential and required for study conduct.

All screening evaluations must be completed and reviewed to confirm that potential participants meet all eligibility criteria. The investigator will maintain a screening log to record details of all participants screened and to confirm eligibility or record reasons for screening failure, as applicable.

Participants will be screened within 28 days prior to administration of the study intervention to confirm that they meet the study population criteria for the study. If the time between screening and dosing exceeds 28 days as a result of unexpected delays (eg, delayed drug shipment), then participants do not require rescreening if the laboratory results obtained prior to first dose administration meet eligibility criteria.

A participant who qualified for this protocol but did not enroll from an earlier cohort/group may be used in a subsequent cohort/group without rescreening, provided laboratory results obtained prior to the first dose administration meet eligibility criteria for this study. In addition, other clinical assessments or specimen collections, eg, banked biospecimens, may be used without repeat collection, as appropriate.

Procedures conducted as part of the participant's routine clinical management (eg, blood count) and obtained before signing of the ICD may be utilized for screening or baseline purposes provided the procedures met the protocol specified criteria and were performed within the time frame defined in the [SoA](#).

Every effort should be made to ensure that protocol-required tests and procedures are completed as described. However, it is anticipated that from time to time there may be circumstances outside the control of the investigator that may make it unfeasible to perform the test. In these cases, the investigator must take all steps necessary to ensure the safety and well-being of the participant. When a protocol-required test cannot be performed, the investigator will document the reason for the missed test and any corrective and preventive actions that he or she has taken to ensure that required processes are adhered to as soon as possible. The study team must be informed of these incidents in a timely manner.

For samples being collected and shipped, detailed collection, processing, storage, and shipment instructions and contact information will be provided to the investigator site prior to initiation of the study.

The total blood sampling volume for individual participants in this study is approximately 110 mL (PK sample volume calculated as approximately 78 mL). The actual collection times of blood sampling may change. Additional blood samples may be taken for safety assessments at times specified by Pfizer, provided the total volume taken during the study does not exceed 550 mL during any period of 60 consecutive days.

To prepare for study participation, participants will be instructed on the information in the [Lifestyle Considerations](#) and [Concomitant Therapy](#) sections of the protocol.

